2.3.4 GROUP 2 (CARTO ISOCHRONAL ACTIVATION MAP)

This will be according to standard practice of the operator. Entrainment can be used to guide the appropriate chamber to map. Points are collected using ConfiDENSE continuous mapping and auto-annotation unless the operator deems otherwise. Further manual annotation can be performed as appropriate. When the operator is satisfied adequate number of points have been collected, the time and number of point is noted and a diagnosis is made.

2.3.5 Categorisation of maps

Grade I map - High diagnostic confidence with clear patterns of activation evident;

and operator selects optimal ablation site from the map.

Grade II map - Moderate diagnostic confidence with some regions where activation

is not clearly seen; a single entrainment site requested before first

ablation

Grade III map - Low diagnostic confidence and alternative arm (Ripple/Conventional

activation) or multiple entrainment requested before first ablation

Grade IV map - Non-diagnostic despite all attempts.

Uncategorised - AT terminated or changed during point collection/pacing

3 STUDY OUTCOME MEASURES

PRIMARY ENDPOINT 1) Tachycardia change/termination with first ablation set after map

categorisation.

SECONDARY ENDPOINT 1) Tachycardia change/termination during point collection

2) Tachycardia change/termination during pacing manuoevre

3) Failure to ablate/ change tachycardia with ablation.

4) The need for entrainment mapping.

If tachycardia does not change with the proposed ablation lesion, or changes to another tachycardia, then operators can continue mapping and performing ablation in the patient's best interests.

If the tachycardia changes prior to the first ablation set, or in the event of a grade 3 diagnosis, operators can continue proceed as per individual preference.

3.1 Post ablation map in patients with any linear lesion sets:

The method for confirming block along a linear lesion line is according to operator preference

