1.3 OBJECTIVE

To compare the effectiveness of Ripple Mapping against conventional activational mapping as determined by:

- 1. The operator's confidence in the diagnosis of the mechanism of atrial tachycardia from their first map collected.
- 2. The percentage of cases where the tachycardia changes/terminates with first ablation set after map categorisation.
- 3. The amount of ablation required; the overall procedural time; dependence on entrainment mapping to make diagnosis.

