2. STUDY DESIGN

This is a multi-centre prospective open randomised control study of 100pts comparing RM guided AT ablation against conventional AT ablation.

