2.3.2.4 Avoiding errors with a Ripple Map

A single entrainment after making a diagnosis with the Ripple Map can be reassuring in complex circuits. In complex cases, the potential for dual loop re-entry is relatively common. In these situations ablation of the clinical tachycardia may cause a small change in cycle length when transitioning to the bystander circuit. Unless a multi-electrode catheter, such as a coronary sinus decapole, shows a change in activation pattern, the transition may not be appreciated. Therefore, periodic checking of the cycle length is recommended and if the tachycardia has not terminated after an appropriate number of lesions delivered, a localised re-map with dense acquisition around the region of interest using RM can determine whether the tachycardia has changed.

Finally, if the. bars are moving out of sequence around the chamber randomly, check the cycle length and fiducial reference for changes as the map is unlikely to be interpretable.

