4. DATA ANALYSIS

The following data will be assessed:

Mapping:

1. Number of points

Tachycardia:

- 1. The diagnosis is recorded as either focal (localized reentry) or macro-reentry
- 2. The grade of diagnostic confidence is recorded
- 3. Validation of the diagnosis with change of activation/termination with ablation.
- 4. Number of times entrainment performed

Ablation:

- 1. Location of ablation delivery
- 2. The duration of RF before tachycardia change/termination

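### The primary endpoint rests on a first ablation set that is neither bounded nor recorded before RF starts, so a set extended after failing could count as a success

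*Combined protocol and SAP*

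**What the plan says.** Section 1.3 (objective 2) gives the primary measure, which section 3 repeats as the sole primary endpoint: "The percentage of cases where the tachycardia changes/terminates with first ablation set after map categorisation". No section bounds the set by site, line, number of lesions, RF time or stopping point.

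Section 3 then uses a different unit: "If tachycardia does not change with the proposed ablation lesion, or changes to another tachycardia, then operators can continue mapping". It does not say that the proposed lesion and the first set are the same thing, or how the endpoint is scored once the proposed lesion has failed.

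On who chooses the target, section 2.3.5 says of a Grade I map: "and operator selects optimal ablation site from the map". Section 2 describes the design: "This is a multi-centre prospective open randomised control study of 100pts". No blinded or independent assessment of the endpoint is described. For the control arm, section 2.3.4 says: "This will be according to standard practice of the operator".

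Among the ablation data, section 4 lists "Location of ablation delivery" and the RF duration up to change or termination. It also lists the diagnosis, the confidence grade and whether the response to ablation validated the diagnosis. It does not list the planned target or the moment at which the first set ended.

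**The concern.** The endpoint stands in for whether the map led the operator to the right place. It does so only if the ablation credited to the map is what the map proposed. Suppose a planned line fails and is then lengthened, widened or joined by a second line nearby until the tachycardia changes. Under the present wording that case could be entered as a first-set success or as a failure, and both entries would be consistent with the protocol.

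The person best placed to make that call is the operator, who knows the arm. If the set is closed more generously in one arm, the primary comparison is biased. If it is closed equally generously in both, the difference between arms shrinks and power is lost. Because the planned target is not among the listed data, an analyst could not reliably tell the two kinds of success apart afterwards.

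**Working it through.** **Inputs from section 7 and the protocol summary.** Control rate 50%, experimental rate 80%, two-sided 5% level, 80% power, minimum 36 per group (72 in total), planned recruitment 100 at 1:1, so 50 per arm.

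**The plan's own figure.** With the unpooled normal approximation, n per arm = (0.5 × 0.5 + 0.8 × 0.2) × (1.960 + 0.842)² / 0.30² = 35.76, which rounds up to 36 per arm and 72 in total. The stated figure is reproduced, and this point does not alter it.

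**Effect of an open boundary.** Let p be the true success rate and r the share of true failures recorded as successes because the set was extended. The recorded rate is p + (1 − p) × r. The documents give no value for r, so 0% to 30% is an assumed range. I also assume that all 50 patients per arm contribute to the endpoint. Section 7 names no test for a binary outcome, so I used the two-sided uncorrected chi-square test, with rejection probabilities from exact binomial enumeration.

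(a) No true difference (50% in both arms), conversion in the Ripple arm only:

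| r | Ripple v control | Chance of a significant result |
|---|---|---|
| 0% | 50% v 50% | 5.7% |
| 10% | 55% v 50% | 8.8% |
| 20% | 60% v 50% | 18.4% |
| 30% | 65% v 50% | 34.3% |

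Under no true difference the arms are interchangeable, so conversion in the control arm only gives the same probabilities with the sign reversed.

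(b) True 50% v 80%, the same conversion in both arms:

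| r | Control v Ripple | Difference | Power |
|---|---|---|---|
| 0% | 50% v 80% | 30 points | 89% |
| 10% | 55% v 82% | 27 points | 84% |
| 20% | 60% v 84% | 24 points | 78% |
| 30% | 65% v 86% | 21 points | 70% |

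(c) True 50% v 80%, conversion in the control arm only: recorded rates of 55%, 60% and 65% v 80% at r = 10%, 20% and 30%, with power of 77%, 60% and 39%.

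**In patients.** At 50 per arm, five reclassified cases move an arm by 5/50 = 10 points, one third of the 30-point design difference.

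**The case against.** The best reply is that section 3 already answers the point. It speaks of a proposed lesion, so a target exists before RF, and Grade I in section 2.3.5 has the operator pick the site from the map. On a natural reading, whatever follows a failed proposed lesion is clinical care after the primary test is over. This stands in part: the plan does contemplate a target. But it does not require the target to be recorded, and it does not say that the endpoint closes as a failure at that point.

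Other safeguards also count for something. Section 2.3.1 requires the same RF catheter approach and settings in both groups, though whether that covers the extent of ablation is arguable. Objective 3 in section 1.3 compares the amount of ablation between arms, which could hint at an imbalance but does not score the endpoint. Change or termination is itself fairly objective; what is open is whether it fell within the first set. The case report form is not among the documents and may capture more than section 4 lists.

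Three stronger readings are tempting and are not supported:

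- A reader might infer that the protocol gives the operator the decision on where the set ends. No sentence assigns it. This is an inference from the open design, from the operator's role, and from the absence of any rule or adjudicator.
- A reader might infer that the bias favours Ripple Mapping. Nothing shows that misclassification would occur or which arm it would favour.
- A reader might take the Ripple section's phrase "if the tachycardia has not terminated after an appropriate number of lesions delivered" (section 2.3.2.4) as a looser scoring rule for that arm. It is technique advice about unnoticed transitions in dual-loop re-entry, and it does not define the endpoint.

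**Conclusion.** The gap is real and worth closing, as a cheap improvement rather than the correction of a demonstrated bias. The unit that decides success is unbounded, the proposed target need not be saved, and the listed data would allow only a partial reconstruction.

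The size is illustrative only. At an assumed 20% conversion the consequence ranges from a roughly threefold rise in false-positive risk (one arm only, no true difference) to power just under the planned 80% (both arms equally); at 10% in both arms power stays above 80%. These figures rest on assumed conversion rates, 50 evaluable patients per arm, and the premise that ablation beyond the proposed set can itself change the tachycardia. The stated sample size is unaffected.

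**What to change.** Add one paragraph to section 3, worded identically for both arms:

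- **When to mark.** After map categorisation and after any entrainment or additional mapping requested before first ablation (Grades II and III), but immediately before the first RF application, the operator marks the proposed first set on the CARTO map and saves it. The mark is a focal site, or a line with both anchors. Placing it after the pre-ablation entrainment matters, because otherwise Grade II cases could be wrongly scored as failures.
- **How to score.** The primary endpoint is a success only if change or termination occurs during RF within the saved set. RF outside it, or after any re-map or entrainment performed once RF has started, counts as after the first set.
- **What it does not touch.** The rule governs scoring only. Clinical management stays with the operator, as section 3 already allows.

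The cost is the paragraph, one saved map tag and one case report form field. Design lines are described in the protocol only as an optional aid in the Ripple section, so the instruction has to be written for the control arm too. The drawbacks are a small recording burden per case and possibly slightly lower success rates in both arms. The operator still draws the mark, so discretion is reduced but not removed.

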3.2 FOLLOW UP

As we are only studying the acute end point of tachycardia termination, no long term follow up data is required. Patients will be followed up as is routine in their Electrophysiology clinic outside of the research protocol. Any redo procedures over the subsequent year should be reported to the trial management team.

4. DATA ANALYSIS

The following data will be assessed:

Mapping:

1. Number of points

Tachycardia:

- 1. The diagnosis is recorded as either focal (localized reentry) or macro-reentry
- 2. The grade of diagnostic confidence is recorded
- 3. Validation of the diagnosis with change of activation/termination with ablation.
- 4. Number of times entrainment performed

Ablation:

- 1. Location of ablation delivery
- 2. The duration of RF before tachycardia change/termination

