7. STATISTICS

Sample Size:

72 patients are required to have a 80% chance of detecting, as significant at the 5% level, an increase in the primary outcome measure from 50% in the control group to 80% in the experimental

group.

Our retrospective study demonstrated a diagnostic yield using RM compared to standard CARTO activation maps of 80% vs 50% (Jamil-Copley et al. 2013). Assuming the same outcome measures, this study is designed to be sufficiently large to detect a difference between arms with 80% power, at the 5% two-tailed significance level. This requires a 36 patients in each group to give a minimum sample size of 72 patients. We have elected to recruit a total of 100 patients into the study.

Categorical variables will be expressed as percentages. Continuous variables will be expressed as mean ± 1 standard deviation for parametric data and/or median ± interquartile range for non-parametric data. The 2 groups will be compared using a student's t-test for parametric data and Mann-Whitney U-Test for non-parametric data. A value of p<0.05 will be considered significant.

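### Amount of ablation (Objective 3) is listed only as RF time before tachycardia change, which has no value for patients who never change, so the planned test would compare outcome-selected subsets

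*Combined protocol and SAP*

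**What the plan says.** Section 1.3 (Objective) sets out, as its third comparison between arms, "The amount of ablation required; the overall procedural time; dependence on entrainment mapping to make diagnosis". Section 4 (Data Analysis) has two ablation items. One is "Location of ablation delivery", which is not an amount. The other is "The duration of RF before tachycardia change/termination". Total RF time, lesion count and procedure time are not listed; the number of entrainment attempts is.

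Section 3 (Study Outcome Measures) expects failures, since a secondary endpoint is "Failure to ablate/ change tachycardia with ablation". It also says that when the proposed lesion does not change the tachycardia, "operators can continue mapping and performing ablation in the patient's best interests". Section 2.3.5 leaves maps uncategorised when "AT terminated or changed during point collection/pacing".

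Section 7 (Statistics) gives a t-test or a Mann-Whitney test for continuous data. It does not say what happens to a patient without a value. The trial is sized to detect "an increase in the primary outcome measure from 50% in the control group to 80% in the experimental" arm.

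The only instruction to note a time is in section 2.3.4, for Group 2, when point collection ends: "the time and number of point is noted and a diagnosis is made".

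**The concern.** RF time before an event is undefined when the event does not occur. No section assigns such patients a value, censors them or ranks them. A t-test or Mann-Whitney test on the item as listed can therefore use only patients who have a value. Having one depends on tachycardia change, which happens after randomisation and is what the trial expects Ripple Mapping to alter. Randomisation no longer protects that comparison.

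If Ripple Mapping succeeds in some patients in whom conventional mapping would fail, those patients add their RF times to the Ripple Mapping group, while their counterparts drop out of the control group. A technique that reduces ablation overall could then appear to save less than it does, or even to need more. Procedure time, named in the same objective, has no listed variable in either arm.

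**Working it through.** **Step 1: the plan's own figure.** With 50% v 80%, 80% power and two-sided 5%, the unpooled formula gives n = (z₀.₉₇₅ + z₀.₈₀)² × (0.5×0.5 + 0.8×0.2) / 0.3² = 7.849 × 0.41 / 0.09 = 35.76. That is 36 per arm and 72 in total, as section 7 states. The planned 100 patients at 1:1 give 50 per arm.

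**Step 2: who has a value.**

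| Course of the patient | Value of the listed RF item |
|---|---|
| Changes during the first ablation set | Defined |
| First set fails, later ablation changes it | Defined only if the item covers later ablation |
| Ablated, never changes | None |
| Changed during point collection or pacing | Unclear (zero or missing) |
| Never ablated, unchanged | None |

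**Step 3: size on the first-set reading.** Applying the design rates to all 50 patients per arm, 0.5×50 = 25 control and 0.8×50 = 40 Ripple Mapping patients have a value; 25 and 10 do not.

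**Step 4: direction on the first-set reading.** The documents give no RF times, so all minutes here are assumptions. Suppose 50% of patients succeed in either arm after 5 min, a further 30% succeed only with Ripple Mapping after h min, and each failure receives 20 min.

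- Patients with a value: control = 5; Ripple Mapping = (0.5×5 + 0.3h)/0.8.
- All patients: control = 0.5×5 + 0.5×20 = 12.5; Ripple Mapping = 0.5×5 + 0.3h + 0.2×20 = 6.5 + 0.3h.

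| h (min) | Ripple − control, patients with a value | Ripple − control, all patients |
|---|---|---|
| 15 | 8.75 − 5.00 = +3.75 | 11.0 − 12.5 = −1.5 |
| 10 | 6.88 − 5.00 = +1.88 | 9.5 − 12.5 = −3.0 |
| 5 | 5.00 − 5.00 = 0 | 8.0 − 12.5 = −4.5 |
| 4 | 4.62 − 5.00 = −0.38 | 7.7 − 12.5 = −4.8 |

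The restricted comparison is less favourable to Ripple Mapping than the all-patient comparison in every row. The expected means reverse only when the extra successes need more RF than the common ones.

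In 4,000 simulated trials (50 per arm, times as medians, log-normal with SD 0.5 on the log scale), the two mean differences pointed opposite ways, against Ripple Mapping in the restricted set, in 94% of trials at h = 10, 77% at h = 15, 51% at h = 5 and 30% at h = 4.

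**Step 5: the wider reading.** Let a fraction f of first-set failures, the same in both arms, change with later ablation, and so contribute their full RF time.

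- With 3 min (common successes), 7 min (extra successes) and 10 min (failures), the means among patients with a value are (3 + 10f)/(1 + f) in control and (3.6 + 2f)/(0.8 + 0.2f) in Ripple Mapping.
- f = 0: 3.0 v 4.5, against Ripple Mapping.
- f = 0.4: 7.0/1.4 = 5.0 v 4.4/0.88 = 5.0, a tie.
- f = 0.8: 11/1.8 = 6.1 v 5.2/0.96 = 5.4, in favour of Ripple Mapping.
- f = 1: 6.5 v 5.6, which is the all-patient result.
- With 5, 10 and 20 min instead, the tie comes at f = 0.2: 9/1.2 = 7.5 v 6.3/0.84 = 7.5.

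In these examples the distortion shrinks as fewer patients lack a value, and is gone when none do.

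**The case against.** The strongest counter-argument is that the RF item is not restricted to the first ablation set, and section 3 lets ablation continue after a failed set. A reader might infer that half of control and 20% of Ripple Mapping patients have no value. The documents support that only on the first-set reading, because 50% and 80% are assumed rates for the first-set endpoint. On the wider reading only never-changers lack a value, and no rate for them is given. This stands and limits the size that can be claimed. The item does not say which reading applies, which is itself a gap.

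A reader might also infer that the comparison will reverse. That is not supported: every minute above is assumed, and nothing in the documents shows that the extra successes would need more RF. The rationale in section 1.1, that Ripple Mapping identifies critical isthmuses, could suggest the opposite. Reversal is possible, not established.

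Nor do the documents show that total RF or procedure time goes uncollected. The section 4 list is not stated to be exhaustive, section 8 promises a complete dataset for randomised patients, and no case report form is included. What can be said is that the plan does not specify these variables. The time noted for Group 2 marks the end of point collection, so it says little about procedure time.

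What survives is that never-changers have no value on either reading, and no section says how to analyse them.

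**Conclusion.** The point holds in limited form. The one listed measure of ablation quantity cannot support the comparison in Objective 3, because whether a patient has a value depends on a post-randomisation outcome expected to differ between arms. On the first-set reading the imbalance is about 25 v 40 patients with a value; on the wider reading it is smaller and cannot be quantified from the documents. The bias needs some patients to lack a value; a reversal also needs particular RF times. Missing procedure time is a lesser gap of specification.

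The primary endpoint and sample size are untouched, and neither amount of ablation nor procedure time is a listed primary or secondary endpoint. This should be corrected, but it does not threaten the main result.

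**What to change.** In section 4, define the amount of ablation as total RF time delivered, for the first set and for the whole procedure, in every randomised patient, counted as zero if no RF was delivered. Compare arms with the Mann-Whitney test already planned. This gives a value to patients whose tachycardia changed before ablation and to those never ablated.

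Total RF credits an abandoned failure with less ablation, so add a sensitivity analysis that ranks patients whose tachycardia did not change as worst. Keep RF time to change as a descriptive measure in patients who changed, and state whether it covers the first set only. Censoring non-changers at the end of the first set is less attractive, because the decision to stop may itself reflect that the lesions were not working. Add overall procedure time for both arms.

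The cost is a few data fields and slightly more analysis, with no change to treatment or sample size. The all-patient test may have little power: in the simulation above, it favoured Ripple Mapping significantly in 21% of trials at h = 10 and 69% at h = 5. The result should be reported as an estimate with its uncertainty.

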5. PARTICIPANT ENTRY

5.1 PRE-REGISTRATION EVALUATIONS

The direct care team will identify potential study patients against inclusion and exclusion criteria, before the Investigator determines their eligibility for participation. The Investigator will discuss the rationale for the study, study procedures, risks and benefits and all other issues mandated by the consent process. The potential participant will be offered an opportunity to participate in the study and written informed consent will be obtained if they agree. Study procedures and assessments will only be performed after written informed consent has been obtained. Patients recruited to this study will not need to undergo any additional investigations above what is required for a standard AT ablation procedure. The informed consent process and all study assessments will be documented in the patient's medical notes and study case report forms.

